We recently completed the first RCT of **Dutasteride for the reduction of heavy** drinking in men. Results support further examination of dutasteride as a treatment option for AUD. In total 189 treatment seeking men were enrolled of which 24 were screen failures and 23 failed to return for the baseline visit leaving 142 subjects randomized to medication (dutasteride n=74). Seven subjects did not return after the baseline randomization visit providing a modified intention to treat sample of 135 subjects (68 dutasteride and 67 placebo) who provided drinking data post-randomization. One hundred seven subjects completed the entire 12-week treatment. The mean number of treatment weeks completed were not different between arms (dut 10.2 vs. pbo 10.7). 3α androstanediol glucuronide levels were decreased by 80% in the dutasteride group at both 6 and 12 weeks vs. 0% in pbo treated subjects confirming the anticipated pharmacological effect for our study design. There were no significant differences between groups (dutasteride vs. pbo) for measures of alcohol consumption during the 60-days prior to screening including the number of standard drinks (SD) per week (48.8 vs. 47.3), number of heavy drinking days (HDD, 5 or more drinks for men) per week (5.2 vs. 5.2), or abstinent days per week (0.67 vs. 0.62). While the dutasteride group were more likely to have had a prior episode of treatment for alcohol use (59% vs. 40%, p=0.03) the number of DSM-IV AD criteria did not significantly differ between groups (4.3 vs. 4.0).

[figure not shown]
Safety. There were no study related serious adverse effects. The proportion of subjects exposed to study medication who reported at least one non-serious adverse

[figure not shown]
effect was not significantly different for the dutasteride vs. pbo groups 71.6% vs. 67.1% similarly, the number of side effects per subject was not different between dutasteride and placebo groups, 1.36 ± 1.46 vs. 1.03 ± 1.10 . Adverse events that were reported by more patients in the dutasteride compared with the placebo arm included stomach discomfort (16.4% vs. 4.5%, p=0.04) and reduced libido (9.0% vs. 0%; p=0.03). More subjects in the dutasteride arm (n=4) than the pbo arm (n=1) stopped medication due to side effects. Beck Depression Inventory scores were low in both treatment arms at baseline (10.4 dut vs. 7.5 pbo) and reduced to a similar degree during the 12-week treatment (-3.3 dut vs. -2.4 pbo, t=0.6; p=0.5).

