2.C.4.b. Visit 2 (Baseline Visit): 3-21 days after the screening visit, eligible subjects will return for their baseline visit. Subjects will be instructed in the use of study medication and will take one capsule study medication (0.5 mg dutasteride or pbo) at the baseline visit and again on study day 2, followed by 2 capsules daily for the remainder of the phase 1 12-week treatment period (in order to match capsule number for 2 day naltrexone titration in phase 2). Finally, subjects will be trained to use a paper calendar provided by staff to record their daily drinking and use of the IVR system to record their mood, desire to drink, self-efficacy and daily drinking during weeks 1-4 and 9-12 of phase 1 and 21-24 of phase 2. We considered asking subjects to use the IVR report daily for the 168 days of treatment but considered that this would be an excessive subject burden.

Study visits beyond visit 2, may be conducted remotely by telephone if a participant is unable to come to the clinic due to illness, travel, or other valid concerns (e.g. about exposure to COVID-19) related to traveling to UConn Health. Participants will be sent a one-time use REDCap secure link via email to complete study visit surveys. In the event a

participant is unable to attend an in person scheduled visit, backup supply of medication previously provided may be used or additional medication (up to 8 weeks) will be provided at an earlier visit if inability to attend future scheduled visit is anticipated in advance. Study staff will consult with study physician regarding whether study medication should be continued if a participant reports illness as reason for a missed in person visit. All unused medications will be brought to the next in person study visit.

2.C.4.c. Bi-weekly Clinic or remote Visits 3-14: A brief Timeline Follow-Back (TLFB) interview will be performed to track participants' daily alcohol consumption and medication use since the last study visit, and a trained staff member will deliver the medical management intervention.

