Study Visit	V1 Screen	V2 Baseline	V 3-7	phase 2 baseline	V 9-13	V14	V15-16
Time relative to Medication		Start medication	wks 2, 4,6,8,10	wk 12 end phase 1	wks 14, 16,18,20,22	wk 24 end phase 2	3- and 6- mo follow- up
Medical History, demographics, AUDIT, SCID, FHAM, ACES, TESI, STAI-trait, Clinical screening labs, blood for DNA and research analytes Physical Exam & Clinician review of Medical History	x						

TLFB, PHQ-9, CIWA, MTR	X	Х	X	X	Χ	X	Χ
Vital signs & weight	Х	Х	X	Х	Х	Х	Х
DMQ, AEQ, SIP	Х			Х		Х	Х
Study outcome blood samples	Х		wk 6	Х	wk 18	Х	Χ
Urine drug screen, HCG (women), PACS	Х		wk 6	Х	wk 18	Х	Х
STAI-state, PSS		Х					
STAI-trait, PSS				Х		Х	Х
Daily IVR call		Х	wk 1-4	wk 9-12		wk 21-24	
Side Effect Checklist (SAFTEE)		Х	Х	Х	Х	Х	Х
Medical Management		Х	Х	Х	Х	Х	
Alcohol SCID past 1 month				Х		Х	Х

The IVR system will use the same procedures we have used in the recently completed dutasteride study and prior UConn Health studies of topiramate (Kranzler, Armeli et al. 2016). a) Daily drinking diary: Every evening, as part of the IVR daily diary, patients will record their alcohol consumption as the number of standard drinks in each of three categories of alcoholic beverages: beer, wine, liquor. Patients are asked to report separately drinking from yesterday and any drinking during the current day, up until the time of the IVR report. This allows us to examine lagged associations with mood and life event triggers. b) Daily mood: Patients will be asked to rate as part of the daily IVR their mood using an adjective checklist. The checklist consists of 9 adjectives (Larsen and Diener 1992) with each rated on a 5-point scale (0 = "not at all" to 4 = "extremely"). Three adjectives for each of three mood state dimensions provide measures of positive mood, negative mood and activated mood. Subjects will also be asked to report their self-efficacy for managing life problems. c) Daily Events: Participants will be asked whether they experienced a list of nine possible daily events (3 stressful, 3 pleasant, and 3 situations where someone might drink). These measures will be used to assess the influence of positive and negative current life events on drinking. d) Drinking motives: Participants will be asked to respond to 3-items for each of three drinking motives as to why they drank today and yesterday; to cope, to enhance or to socialize on a 3-point scale (1= "not at all", 2="somewhat" and 3="definitely).

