The timeline follow back (TLFB) (Sobell and Sobell 1992) will be used to estimate drinking at intake, at each biweekly study visit during the active treatment period and at the 3- and 6-month follow-up evaluation. This interview procedure will provide quantity/frequency of alcohol consumption data for each day since the last study visit. Time since onset of last menses will be collected at each treatment visit for women to examine as a co-variate for medication effects and safety monitoring for pre-menstrual women. Medication adverse effects: Subjects will provide reports of side effects at each bi-weekly study visit and the 3- and 6-month follow-ups using the widely used Systematic Assessment for Treatment Emergent Effects (SAFTEE) (Levine and Schooler 1986, Johnson, Ait-Daoud et al. 2005).

Measures of treatment received (MTR): All medication taken will be recorded. The study staff will also record the number of contact hours subjects have been exposed to for any treatment outside of the study that is related to their drinking to identify if this variable might need to be considered as a covariate in outcomes analysis.

2.C.7. Genotyping: Genotyping for urn randomization will be done using Cells-to-Ct assay reagent (Applied Biosystems, Inc) to allow genotyping at the *FKBP5* rs1360780 SNP directly from blood. The anticipated genotype distribution frequency based on our study of 1845 college students (Lieberman, Armeli et al. 2016) and the 1000 genomes project is CC 0.48 and T-carrier 0.52 for Caucasians and 0.37 and 0.63 for African-Americans. Reference DNA samples representing each of the three possible genotypes at rs1360780 will be included with each subject sample. Additional DNA will be purified from whole blood using the PureGene kit (GentraSystems, Minneapolis, MN) to allow confirmation of initial rapid genotyping for urn randomization using batched purified DNA samples. In view of advances in knowledge during the time of this study we anticipate that DNA will also be used to examine genotypes at other candidate markers related to alcohol use and related behaviors.

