2.C.8 Exploratory microbiome analysis Leclercq et al (Leclercq, Matamoros et al. 2014, Leclercq, de Timary et al. 2017) have reported that as many as 40% of alcohol dependent subjects may harbor pro-inflammatory gut microbiota contributing to increased gut permeability which was associated with higher anxiety and alcohol craving after 3 weeks of abstinence. Our hypothesis is that participants with higher levels of pro-inflammatory gut microbes at baseline will have less success in reducing drinking. Stool samples will be collected by participants at home and transported to the CRC in a small cooler with freezer packs. Samples will be stored at -80C until batch processed. DNA will be prepared from stool samples and used for metagenomics whole genome shotgun sequencing of microbial DNA. This method allows species and strain level identification of the gut microbiome. Analysis of sequence data and comparison of strains by treatment response will be done by [name] Assistant Professor of Medicine at UConn Health who is an experienced investigator in molecular characterization of human microbiomes. Correlations of the relative abundance of microbes in baseline stool samples with participant success and in reducing weekly drinking will be examined. We will also examine change in microbiome between baseline and endpoint as a function of change in drinking.

2.C.9. Data Analysis:

2.C.9.a.1. Safety: Safety will be analyzed using categorical outcomes, defined by the type and severity of adverse effects. Summary measures of adverse effects (AEs) will be developed by organ system from the SAFTEE adverse event checklist and will be compared for patients receiving dutasteride or pbo using χ^2 analysis in phase 1 and

comparing patients switched to dutasteride vs. naltrexone in phase 2. Comparisons will be conducted on 1) the proportion of patients in each of the comparison groups who report AEs, 2) the proportion of patients in each of the comparison groups who report moderate-to-severe AEs, and 3) the proportion of patients in each comparison group who discontinue treatment due to AEs. Individual AEs that occur in \geq 5% of patients in either medication condition will be examined using χ^2 analysis.

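### The safety analysis sets no new-or-worse condition against the SAFTEE already scheduled at the first-dose visit, which can dilute the phase 1 adverse event comparisons and bias the phase 2 one

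*Combined protocol and SAP*

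**What the plan says.** Section 2.C.9.a.1 (Safety) names the source of the events: "Summary measures of adverse effects (AEs) will be developed by organ system from the SAFTEE adverse event checklist". It then lists three comparisons, dutasteride vs placebo in phase 1 and switched-to-dutasteride vs switched-to-naltrexone in phase 2. The first is "Comparisons will be conducted on 1) the proportion of patients in each of the comparison groups who report AEs". The second is the same for moderate-to-severe AEs. The third is "the proportion of patients in each comparison group who discontinue treatment due to AEs". Individual AEs that reach "5% of patients in either medication condition will be examined using" a chi-square test. None of these sentences mentions a baseline reading.

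A baseline reading is nevertheless planned. In Table 2 (Schedule of Assessments) the row "Side Effect Checklist (SAFTEE") is blank at Visit 1 and marked from Visit 2 onward. Visit 2 is the first-dose visit: under 2.C.4.b subjects "take one capsule study medication (0.5 mg dutasteride or pbo) at the baseline visit". The documents do not say whether the checklist comes before or after that capsule. Section 2.C.6.b.4 describes collection as "Subjects will provide reports of side effects at each bi-weekly study visit and the 3- and 6-month follow-ups", without naming Visit 2.

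**The concern.** A symptom checklist records what patients have, not what the drug caused. Three records show the difficulty. One patient has stomach discomfort at Visit 2 and the same discomfort through week 12. A second has none at Visit 2 and develops it at week 4. A third has low libido at every visit, including Visit 2. Under the literal wording all three are patients who report an AE, and only the second shows something that began on treatment.

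Aim 1 hypothesizes that dutasteride is well tolerated by men and women. A background of pre-existing symptoms pushes the phase 1 comparison toward finding no difference, which would be read as support for that hypothesis. For efficacy, by contrast, 2.C.9.a.2 adjusts explicitly for pretreatment drinking.

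Phase 2 raises a separate issue. The group switched to naltrexone has had 12 weeks of dutasteride, and the group switched to dutasteride has had placebo. Randomization does not balance symptoms carried over from phase 1 between these groups.

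**Working it through.** **Does another section supply the missing condition?** Section 3.C says AEs are graded and assigned causality, but 2.C.9.a.1 does not use that rating. Section 2.C.6.b.4 speaks of side effects without defining them, and treatment emergence appears there only in the instrument's name. Section 3.C applies SAFTEE at every treatment visit, and 2.C.3.a calls Visit 2 the first treatment visit, so a literal reader could even count the Visit 2 reading as an AE. No section brings in a baseline condition.

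**The documents' own figures.** No power is stated for safety. Section 2.B.2 reports, from the first trial, "stomach discomfort (16.4% vs. 4.5%, p=0.04) and reduced libido (9.0% vs. 0%; p=0.03"). Counts inferred from the percentages are 11/67 vs 3/67 and 6/67 vs 0/67. Fisher's exact test gives p=0.045 and p=0.028, which agrees with the stated 0.04 and 0.03.

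**Formulas.** Let q be the share of patients with the symptom at Visit 2, equal in both arms by randomization, and e the new-onset rate among the rest.

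- Any report counts: rate = q + (1−q)e.
- Only symptoms absent at Visit 2 count, all patients in the denominator: rate = (1−q)e.

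Either way the arm difference is (1−q)(e1−e0). With all patients in the denominator, the proposed count does not undo that shrinkage. What it removes is the background q added to both arms, which raises the variance. The two counts must therefore be compared at the same q.

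**Inputs.** 95 per arm (Table 1); e1=16.4% and e0=4.5% (2.B.2, assumed here to be new-onset rates); uncorrected chi-square at two-sided 0.05 (assumed, since no safety alpha is stated); exact binomial power; worsening not counted. The values of q are assumptions.

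| q | Any report: rates | Difference (points) | Power, any report | Power, absent at Visit 2 |
|---|---|---|---|---|
| 0 | 16.4% vs 4.5% | 11.9 | 80% | 80% |
| 4.5% | 20.2% vs 8.8% | 11.4 | 62% | 78% |
| 10% | 24.8% vs 14.1% | 10.7 | 47% | 75% |
| 20% | 33.1% vs 23.6% | 9.5 | 31% | 69% |

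Example at q=10%: 0.10 + 0.90×0.164 = 0.248 and 0.10 + 0.90×0.045 = 0.141.

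**No true difference.** With e=10% in both arms, rejection stays at about 5% under either count for q up to 30%.

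**Any-AE comparison.** With assumed new-onset rates of 50% vs 30%, power when counting any report falls from 81% at q=0 to 60% at q=20% (60% vs 44% observed) and 41% at q=40% (70% vs 58%).

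**Phase 2.** Suppose non-responders carry stomach discomfort into phase 2 at the first trial's rates and a fraction s of those symptoms persists. The naltrexone group then starts with a rate 16.4s − 4.5s = 11.9s points higher, before any phase 2 capsule. At s=1 and the group sizes in Table 1, that is about 0.164×40 = 6.6 patients on naltrexone against 0.045×64 = 2.9 on dutasteride. Both s and the use of these rates for non-responders are assumptions.

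**The case against.** The strongest reply is that the plan is silent rather than wrong. It speaks of adverse effects and side effects, grades events and assigns causality. A Visit 2 checklist also fits an intended baseline reference. A reader might infer that the plan counts every SAFTEE report as a drug effect. The documents do not say so. The any-report count is the literal reading of a rule with no baseline condition, and in a randomized phase 1 comparison pre-existing symptoms raise both arms without creating a drug effect.

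The reply also limits the size. If the first trial counted every report, its placebo rates bound q for these items. Zero of 67 for reduced libido gives a 95% upper limit of 1 − 0.05^(1/67) = 4.4%. For stomach discomfort, three or fewer of 67 has probability 0.09 at q=10% and 0.0003 at q=20%. In that case 16.4% vs 4.5% would already include any background, and any-report power with 95 per arm would be the 80% in the first row. If instead the first trial counted only new events, no bound on q follows, but the same group was then already applying a rule that this plan leaves out. Section 2.B.2 does not say which. That trial enrolled men only, whereas about 35% women are expected here, so the bounds do not carry over firmly. For any-AE, a placebo rate of 67.1% hardly bounds q.

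What stands of the objection is that the higher values of q are illustrations and that a hidden difference is possible, not shown. The objection does not supply the missing condition.

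**Conclusion.** The gap is real and worth closing. The comparisons of any AE, moderate-to-severe AEs and individual AEs, including the 5% screen, carry no new-or-worse condition, although the reading needed for one is scheduled. In phase 1 the consequence is loss of sensitivity, not a false signal. For a difference like that seen for stomach discomfort, the loss relative to the proposed count is about 16 points of power at q=4.5% and 28 at q=10%, if the first trial's rates are new-onset rates and every report counts. The true q is not in the documents.

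Two stronger readings are not supported. One is that the plan will hide a real tolerability difference: that depends on an unknown q, and the first trial found two item-level differences with about 67 per arm. The other is that every tolerability comparison is affected: discontinuation due to AEs needs an event after dosing and is essentially untouched.

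In phase 2 the same omission can bias the comparison against naltrexone, because the groups enter with different drug exposure. The direction follows from the design; the size is not known.

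**What to change.** In 2.C.9.a.1, define an analysed phase 1 AE as a SAFTEE item that is absent at Visit 2 and later reported, or reported at a higher severity than at Visit 2. State that the Visit 2 SAFTEE is completed before the first capsule. Apply the definition to the any-AE, moderate-to-severe and individual-AE comparisons, including the 5% screen. For phase 2, use the Visit 8 SAFTEE, completed before the first phase 2 capsule, as the reference in the same way. Tabulate symptoms present at each reference visit, and raw report rates, alongside.

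The cost is a few sentences and a small derivation from data already scheduled, with no added visit or procedure. Headline AE percentages will be lower than raw report rates, which is why both should be shown. The Visit 8 reference removes carried-over reports from the phase 2 count. It does not make the two non-responder groups comparable in other respects, so that comparison should still be described as non-randomized.

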comparison in phase 1 and a within-subjects test in phase 2 for patients treated with pbo in phase 1 and dutasteride in phase 2, iii) allow evaluation of whether reductions in drinking are maintained with ongoing treatment for phase 1 dutasteride responders, and iv) provide preliminary data on whether dutasteride non-responders show reductions in drinking when crossed over to naltrexone, an established medication for AUD with a different mechanism of action compared with dutasteride.

Three and six-month follow-up visits following the completion of the 24-week treatment phase will evaluate the durability of treatment effects, allow measurement of the degree to which dutasteride effects on 5AR inhibition have been reversed following 12- or 24-week exposures and to maintain contact with female participants to remind them of the importance of effective contraception for 6 months following treatment.

Table 1. Expected Patient Distribution for Phase 1 and 2.

Phase 1	Phase 1	Phase 1	Phase 2	Phase 2 Statistical contrasts
Treatment	Statistical	Expected Tx	Treatment	
	contrasts	response groups		
Dutasteride n=95 (grp A)	Between-subject contrasts using GLMM Dut vs. Pbo for DVs HDD/wk and SD/wk;.	Dut-R (wk 9-12 Response n=40) Dut-NR (wk 9- 12 Non-Response n=40)	Dut-R dutasteride Dut-NR naltrexone	Within-subject interrupted time series regression using mixed models. Dut-R: Is dut response maintained? Dut-NR: Do dut NRs respond to naltrexone?
	Moderating			
Pbo n=95 (grp B)	effects of genotype, baseline state vs. trait anxiety, perceived stress and interaction with FKBP5 genotype	Pbo-R (wk 9-12 Response n=16) Pbo-NR (wk 9- 12 Non-Response n=64)	Pbo-R pbo Pbo-NR dutasteride	Pbo-R: insufficient sample for statistical comparison. Pbo-NR: Do pbo NRs respond to Dut?

Phase 1 response ≥ 60% reduction SD/wk for wk 9-12 vs baseline (current study 49% response rate for dut vs. 20% pbo). dutasteride 1 mg/day; naltrexone 50 mg/day.

2.C.2. Patients: Drinkers who want to reduce or stop drinking will be recruited using advertisements in radio and print media, by posting/distributing recruitment materials in community settings, informational mailings to area clinicians and by referral from UConn Health medical and dental clinics in at our main campus in Farmington CT together with

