- 2.C.3.d. Medication Randomization and Drug Accountability: Urn randomization (Stout, Wirtz et al. 1994) will be used to assign subjects 1:1 to dutasteride or pbo for treatment phase 1, balancing for number of DSM5 AUD criteria (2-5 vs.>5), DTC relative to total motives score (0-25% vs. >25%), *FKBP5* genotype (CC vs. T-carrier), current smoking status, and use of medication for treatment of co-morbid psychiatric condition. Separate

randomizations will be done for women and men to ensure balance on these variables in both sex groups. At the end of phase 1, patients who have reduced drinks/week by at least 60% will continue for the second 12 wks on the originally randomized treatment taking 2 capsules per day. Subjects who have reduced drinks/wk by less than 60%, will be informed that they will be transitioning to an active study medication (either dutasteride or naltrexone), and will be interviewed to confirm they have not used opioid medication for 5 days prior which will be verified by urine testing, subjects testing positive for opioids will not be eligible for starting phase 2. For non-responder subjects in the phase 1 pbo arm, the pharmacy will begin dispensing 0.5 mg dutasteride capsules with instructions to take 1 capsule per day for 2 days, then 2 capsules daily for 12 weeks. For subjects in the initial dutasteride arm and reducing less than 60%, the pharmacy will dispense 25 mg naltrexone capsules with the same instructions of 1 capsule for days 1 and 2 followed by 2 capsules each day (50 mg naltrexone per day) to match the dutasteride capsule dosing. Medication vials including any unused medication will brought to each follow-up visit. Unused pill counts will be recorded by the study nurse at each bi-weekly visit and medication use recorded daily by patients on their drink log.

2.C.4. Study Visits:

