2.C.9.b. Sample size considerations: For Aim 1, the proposed sample size of 160 completing the phase 1 12-week treatment (80 per arm), has 80% power to show statistical significance (α =0.05) for medium-size effects, d=0.4, such as observed in our initial RCT of dutasteride in men (d=0.38 for change in SDs/wk from baseline to last month of treatment comparing dutasteride and pbo n=91]. For Aim 2a, assuming 80% power and α =0.05 and a sample of 40 responder subjects continuing on dutasteride, the non-inferior margin limit would be an increase of 0.67 HDD/wk or 5 SDs/wk during the second 12 weeks dutasteride treatment. For Aim 2b, a sample of 64 placebo non-responders crossing over to dutasteride for phase 2 would have 90% power to detect a medium effect size for reduction in drinking in phase 2 using a within-subjects t-test. For Aim 3, using the GLMPOWER procedure and the between cell effects for the preliminary data presented above (section 2.B.2) for the 2-way interaction of drinking to cope x drug, a sample of 160 subjects in phase 1 would have 80% power to detect the magnitude of this interaction seen in the preliminary dataset.

Table 3. Timeline for recruitment and other study objectives:

Dutasteride AUD#2 protocok V9 (05-18-2022)

IRB NUMBER: 19-147-2 IRB APPROVAL DATE: 02/27/2024

Staff training & study prep										
Patient enrollment & randomizing 5/mo										
3- and 6-month follow-up										
Data entry & cleaning										
Data analysis & Report writing										

Section 3. PROTECTION OF HUMAN SUBJECTS

3.A Risks to Human Subjects

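### The only planned overall comparison of adverse-event frequency, the any-AE proportion, has about 10% power on the first trial's figures; adding a per-patient event rate would raise this to about 36–42% at almost no cost

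*Combined protocol and SAP*

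**What the plan says.** Section 2.C.9.a.1 (Safety) makes all safety outcomes categorical. It plans:

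- organ-system summary measures built from the SAFTEE checklist, compared by chi-square;
- three proportions: "the proportion of patients in each of the comparison groups who report AEs", the proportion with moderate-to-severe AEs, and the proportion stopping treatment because of AEs;
- a chi-square test of each individual AE that occurs in at least 5% of patients in either condition.

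No count or rate of events per patient is listed, and no power or significance level is given for safety.

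The data for a count will exist. Section 2.C.6.b.4 states: "Subjects will provide reports of side effects at each bi-weekly study visit". The first trial, described in 2.B.2, used such a summary and reported that "the number of side effects per subject was not different between dutasteride and placebo groups", with 1.36 ± 1.46 against 1.03 ± 1.10. For the yes/no version it reported 71.6% against 67.1%, not significantly different. Tolerability in both sexes is part of the Aim 1 hypothesis.

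**The concern.** Reducing repeated checklist data to one yes/no per patient discards the difference between a patient with one event and a patient with four. If dutasteride mainly adds events among patients who would have reported something anyway, the any-AE proportion hardly moves. In the first trial the mean count was 32% higher on dutasteride (1.36/1.03 = 1.32), while the any-AE proportion differed by only 4.5 points.

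The plan therefore has no sensitive summary of overall burden. This matters most for an excess spread over several complaints, or over complaints each below the 5% threshold, which the individual-AE tests are not designed to show. The new trial also expects 35% women (2.C.2), and the first trial enrolled only men, so it is not known in advance which AEs will differ.

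**Working it through.** **Inputs.** Table 1 has 95 per arm randomised. Section 2.C.9.b has "the proposed sample size of 160 completing the phase 1 12-week treatment (80 per arm"). Allocation is 1:1 (2.C.3.d). The AE figures come from 2.B.2. Two assumptions are mine: a two-sided 5% level (2.C.9.b gives 0.05 for Aim 1 without sidedness, and nothing is given for safety), and ± read as a standard deviation.

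**Step 1. The first trial's own results.** The plan has no safety power figure to reproduce, so I checked the reported null results. With arm sizes consistent with 2.B.2, uncorrected chi-square on any AE gives p of about 0.53–0.61, and the Welch t-test on the count gives p of about 0.13–0.14. Both agree with what was reported.

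**Step 2. Power of the any-AE comparison.** Power = Φ[(Δ − 1.96·SE₀)/SE₁], with Δ = 0.716 − 0.671 = 0.045, pooled proportion 0.6935, SE₀ = √(2 × 0.6935 × 0.3065/n) and SE₁ = √[(0.716 × 0.284 + 0.671 × 0.329)/n].

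- n = 95: SE₀ = 0.0669, SE₁ = 0.0668; (0.045 − 0.1311)/0.0668 = −1.29; power 9.9% (10.3% counting both tails).
- n = 80: SE₀ = 0.0729, SE₁ = 0.0728; (0.045 − 0.1429)/0.0728 = −1.34; power 8.9% (9.4% counting both tails).

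About 1,647 per arm would be needed for 80%.

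**Step 3. Power of the per-patient count.** Pooled SD = √[(1.46² + 1.10²)/2] = 1.293 and Δ = 0.33, so d = 0.255. Power = Φ[Δ/(SD·√(2/n)) − 1.96].

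- n = 95: 0.33/0.1876 = 1.76; power 42.1% (41.7% by noncentral t).
- n = 80: 0.33/0.2044 = 1.61; power 36.5% (36.1% by noncentral t).

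About 241 per arm would be needed for 80%.

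**Step 4. Does the loss come from the yes/no cut?** Negative binomial counts were simulated to match the quoted means and SDs, and each data set was analysed in several ways (20,000 data sets per arm size; 4,000 for the rank test).

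| Analysis of the same counts | 80 per arm | 95 per arm |
|---|---|---|
| Any event, chi-square | 9.5% | 10.2% |
| Count, Welch t | 35.9% | 40.5% |
| Count, log rate ratio | 38.0% | 42.5% |
| Count, Mann-Whitney | 23.7% | 25.8% |

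The loss does come from the cut. The matched distributions imply any-event proportions of 65.9% and 61.3%, somewhat below those reported, but the gap of 4.6 points is nearly the same. The gain depends on a mean-based analysis, since a rank test recovers only about half of it.

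**Step 5. The other planned tests.** Normal-approximation power on first-trial figures, unadjusted for multiplicity, over 80 to 95 per arm:

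- stomach discomfort (16.4% vs 4.5%): 69–77%;
- reduced libido (9.0% vs 0%): 79–85%, although with an empty cell this depends on the test used;
- stopping for AEs (4 vs 1 patients): 28–36%, over the possible denominators.

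**Step 6. What the added analysis would show.** If the first-trial figures recurred with 95 per arm, SE(log rate ratio) = √[(1.46²/1.36² + 1.10²/1.03²)/95] = √(2.293/95) = 0.155. The 95% CI around 1.32 would be 1.32 × e^(±0.3045), or about 0.97 to 1.79.

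**The case against.** The strongest reply is that 2.C.9.a.1 already contains sharper tools than the any-AE proportion. In the first trial the individual-AE tests found the signal (p = 0.04 and p = 0.03), while the per-patient count did not (p about 0.14). Step 5 shows those tests would again have good power for the same two complaints. This stands, and it rules out several stronger readings:

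- A reader might infer that the tolerability assessment as a whole has 10% power. It does not. The figure belongs to one comparison among several.
- A reader might infer that the any-AE proportion is near its ceiling. At 67–72% it is not. Power is low because the observed difference was only 4.5 points.
- A reader might infer that a null any-AE result will by itself be taken as proof of good tolerability. No section makes that claim depend on this test, and 2.B.2 reported the null overall result together with the individual excesses and the stops for side effects.
- A reader might infer that the count should lead, with severity and discontinuation made descriptive. The first trial gives no support for that ranking.

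It is also fair to say that 2.C.9.b claims no power for safety, so no stated figure is contradicted.

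The reply does not supply a measure of overall burden. The high power in step 5 is for two AEs singled out because they differed, which makes those effects likely overestimates. No multiplicity control is stated for those tests, and they do not add up an excess spread across complaints.

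**Conclusion.** The point holds for overall AE frequency only. On the first trial's estimates the any-AE comparison has about 9–10% power, and a mean-based analysis of events per patient about 36–42%. The lower end applies if 80 per arm contribute, the upper end if all 95 do.

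These figures rest on a two-sided 5% level, on ± being a standard deviation, and on two non-significant estimates from men only. The gain is real, but power remains below 50%: a non-significant count would still be the more likely result under these assumptions. The value of the addition lies in the estimate and its interval, which show how large an excess burden the data still allow. It is a cheap improvement to the safety section.

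**What to change.** In 2.C.9.a.1, keep every planned comparison at its present standing and add one: the number of treatment-emergent SAFTEE events per patient in phase 1, analysed by negative binomial regression with log weeks observed as offset, reported as a dutasteride/placebo rate ratio with 95% CI. Do the same for moderate-to-severe events. State that the interval, not the p-value, will be interpreted.

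The model family is already in the plan: 2.C.9.a.2 uses a negative binomial with log link for drinks per week. The offset allows for unequal observation. In the first trial, mean weeks completed were 10.2 on dutasteride and 10.7 on placebo; taking these as weeks observed would move the ratio from 1.32 to (1.36/10.2)/(1.03/10.7) = 1.39.

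The cost is a sentence or two and two models, with no new data or patients. There are two downsides. A rule must be written so that an event that persists or recurs across visits is counted once. A raw count also weights mild and severe events equally, which is why the moderate-to-severe version should accompany it.
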